1.5 Risk Benefit Ratio

The potential benefits of this study outweigh the minimal risks to participants.

2 Study Objectives, Aims and Hypothesis

Aim 1A: Perform a multicenter, cluster randomized trial to evaluate the efficacy of a direct gloving strategy to improve compliance with infection prevention practices (i.e. HH and glove use).

Hypothesis: When compared to the standard practice of performing HH and then donning gloves, directly gloving when gloves are indicated will increase compliance with HH and glove use.

Aim 1B: Perform a nested multicenter validation study, where gloved hands of HCWs will be randomly sampled to determine bacterial contamination of non-sterile gloves after donning.

Hypothesis: When compared to the standard practice directly gloving when gloves are indicated will have no effect on bacterial contamination of gloves.

3 Study Design and Procedure

Aim 1A:

Study Design: We will perform a cluster-randomized trial to include 14 patient care areas (i.e. units) at the University of Maryland Medical Center (UMMC), the R Adams Cowley Shock Trauma Center (STC), University of Iowa Hospitals (UIH), and Johns Hopkins Hospital (JHH). Each unit will be randomly assigned to the intervention or usual care group. Randomization will be stratified by unit type: adult intensive care, general pediatric wards, emergency departments and inpatient hemodialysis units. One unit from each of the four types at UMMC, UIH, and JHH will be selected for study participation and will be randomized; and two units (one Adult ICU and the Trauma Resuscitation Unit (comparable to the Adult ED)) will be selected and randomized from Shock Trauma. We have specifically chosen these diverse areas to avoid any potential crossover of effect from one study unit to another as units have very different personnel with very little crossover of care.

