In order to account for differences in baseline compliance with infection control practices including HH and glove use, baseline rates of compliance will be observed across all available units (this includes 4 adult ICUs, 3 general pediatric wards units, 1 ED and 1 inpatient HD unit at UMMC and 4 adult ICUs and 1 ED at Shock Trauma). In the study period prior to randomization; the final units will be selected based on similar baseline compliance. For example, there are 11 general pediatric wards across three sites. Baseline data will be collected and compared across all 11 wards. One pediatric unit from each facility with the closest baseline composite HH and glove compliance rates will be selected. Thus we are matching 3 general pediatric wards (one from each site) based on pre-intervention outcomes of interest to improve power and minimize the impact of measured and unmeasured confounders. Once selected, the units will be randomized to the intervention or usual care group. This process will be done for each unit type (e.g. adult ICU).

The study will begin with a 6-month period of baseline data collection in which HH and infection prevention compliance will be recorded in all units that are potentially available for inclusion as described above. During that time period the investigative team will develop and refine educational, training and data collection tools. Following this baseline period, a short “wash-in” period of 3 months will be used to educate and train HCWs in the participating units regarding expected infection prevention practices of HH and glove use. The intervention period will be a full 12 months. This will allow the intervention to be tested over a full calendar year accounting for differences in seasonality as well as different levels of training across an academic year.

All participating units regardless of intervention status will receive education regarding policies and procedures for compliance with infection prevention strategies including HH and glove/gown use. This education will be identical in both groups (intervention and usual care) and will be consistent with published guidelines (WHO/CDC) with the exception of HH prior to donning non-sterile gloves - which according to existing guidelines is an uncertain area where research is needed. HCWs from units randomized to the usual care group will receive education that states that they should perform HH prior to donning non-sterile gloves. HCWs from units randomized to the

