6.2 Sample Size Estimates

Aim 1A:

How many participants (or specimens, or charts) will be used in this study?

UMMC: 6 units Worldwide: 14 units

14 units will be randomized to intervention or usual care. Over the 12-month study period we expect a minimum of 7000 total observations (14 units across the systems x 500 observations). Each system will have a research coordinator perform observations 3 hours per day four days per week. We estimate an average of 5 observations per hour¹⁹ (15 per day and 60 per week) and thus over 2500 observations per year per research coordinator are feasible (we expect to require fewer to achieve desired power). Average HH compliance is consistently at 40-50% and are often lower when glove use is indicated^{1,15}, we believe the compliance with infection prevention practices (i.e. primary outcome, composite compliance with HH AND glove use) in the usual care group will be ~40%. Recent studies have shown compliance with gloves when indicated to be approximately 70-80%¹⁵. Thus for the primary outcome, we expect a difference in compliance with infection prevention practice to be ~ 30%. If we assume 500 observations per area, an alpha level of 0.05, an interclass coefficient of 0.001²² we will require inclusion of 4 patient care areas (2 experimental and

2 usual care) to achieve a power greater than 90% power to detect an effect size of 30% (i.e. the primary outcome). If we vary the interclass coefficient to 0.01, we still have greater than 90% power under the same conditions. Relative to the secondary outcome, in which we will compare compliance with gloving only in both the direct gloving (i.e. experimental group) and the usual care group, we believe it is reasonable to expect that removing the cumbersome and time-consuming requirement of HH prior to glove use may increase compliance with glove use when indicated by approximately 10%. Using the same assumptions as the primary aim with an interclass coefficient of 0.001, we need to recruit and randomize 4 participating units to achieve > 90% power to detect this effect size of 10%. If we use the higher interclass coefficient of 0.01, we need 8 participating units to achieve > 85% power. So in short, we have ample power to see an effect in both primary and secondary outcomes including the sub-populations of adult ICU, dialysis and emergency department.

Aim 1B:

How many participants (or specimens, or charts) will be used in this study?

Local: 866 Worldwide: 2600

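### Section 6.2 claims ample power in adult ICU, dialysis and ED with no ICC condition, but its own figure for glove use at ICC 0.01 is 8 units and these types have 4, 3 and 4

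*Combined protocol and SAP*

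**What the plan says.** Section 6.2 (Aim 1A) assumes 500 observations per unit, alpha 0.05 and an ICC of 0.001, and then varies the ICC to 0.01. For the primary composite (about 40% in usual care, a 30-point difference) it states more than 90% power with 4 units, 2 per arm, at both ICCs.

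For glove use alone it expects a gain of about 10% and gives two requirements. At ICC 0.001, "we need to recruit and randomize 4 participating units to achieve > 90% power to detect this effect size of 10" percent. At ICC 0.01, "we need 8 participating units to achieve > 85% power". The baseline is indicated by "Recent studies have shown compliance with gloves when indicated to be approximately 70-80" percent.

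The next sentence sums up: "we have ample power to see an effect in both primary and secondary outcomes including the sub-populations of adult ICU, dialysis and emergency department".

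The unit counts are in Section 3 (Aim 1A): "One unit from each of the four types at UMMC, UIH, and JHH will be selected", and "two units (one Adult ICU and the Trauma Resuscitation Unit (comparable to the Adult ED)) will be selected and randomized from Shock Trauma".

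**The concern.** The summing-up sentence drops the ICC condition that the sentence before it had just introduced, and it carries the claim from the whole trial down to three unit types. Each of those types has at most half of the 8 units the plan asks for at ICC 0.01. For dialysis, even the plan's lower 4-unit requirement is not met.

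What is at stake is interpretation. A protocol that promises ample power within adult ICU, dialysis and ED invites a reader to take a non-significant glove-use result in one of them as evidence that direct gloving has no effect on glove use there.

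**Working it through.** **Units per type (Section 3).** Three hospitals each give one unit of each type, and Shock Trauma adds one adult ICU and one ED-type unit. Adult ICU 3 + 1 = 4; ED-type 3 + 1 = 4; dialysis 3; general pediatrics 3; total 14, as stated.

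**Inputs from Section 6.2.** 500 observations per unit; alpha 0.05; ICC 0.001 or 0.01; glove-use baseline 70-80%; gain 10%.

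**Assumptions, because the plan does not state them.** Normal test, two-sided; the gain is in absolute percentage points; 2+2 allocation in 4-unit types and 1+2 or 2+1 in the 3-unit type; no gain from matching or covariate adjustment.

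**Formulas.** With k0 control units and k1 intervention units:
- DEFF = 1 + 499 × ICC, which is 1.499 at ICC 0.001 and 5.99 at ICC 0.01.
- SE = √[DEFF/500 × (p0(1−p0)/k0 + p1(1−p1)/k1)].
- Power = Φ(difference/SE − 1.960).

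**Reproducing the plan's figure (8 units, 4+4, 70% v 80%, ICC 0.01).** SE = √[5.99/500 × (0.21/4 + 0.16/4)] = √(0.01198 × 0.0925) = 0.0333. Difference/SE = 3.004; 3.004 − 1.960 = 1.044; power 85.2% (84.9% with pooled variance). This agrees with the stated figure of more than 85%. One-sided 0.05 would give 91%, so two-sided fits better.

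**Same formula at the unit-type counts, 70% v 80%, ICC 0.01.**
- 2+2: SE = √(0.01198 × 0.185) = 0.0471; 2.124 − 1.960 = 0.164; power 56.5%.
- 1 control + 2 intervention: SE = √(0.01198 × 0.29) = 0.0589; 1.697 − 1.960 = −0.263; power 39.6%.

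Over the baseline range, glove use at ICC 0.01, two-sided:

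| Units (control + intervention) | 70 v 80% | 75 v 85% | 80 v 90% |
|---|---|---|---|
| 2+2 (adult ICU, ED) | 56.5% | 63.4% | 73.4% |
| 1+2 (dialysis) | 39.6% | 44.5% | 52.3% |
| 2+1 (dialysis) | 42.7% | 49.3% | 60.1% |
| 7+7 (whole trial) | 97.8% | 99.1% | 99.8% |

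**Sensitivity.**
- One-sided 0.05: 68-83% with 4 units, 52-72% with 3.
- Effectively unlimited observations per unit, two-sided: at most 64-81% and 46-68%. The limit is the number of units, so more observation would not cure it.

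**The other scenarios, same normal approximation.** Glove use at ICC 0.001: 99% or more with 4 units, 92-99% with 3. Composite 40% v 70%: above 99% with 3 or 4 units at both ICCs.

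**How far that approximation can be trusted with 3 or 4 units.** Section 6.1 places the analysis at unit level and names GEE without a small-sample correction. As an assumed alternative, take a t reference with (units − 2) degrees of freedom and noncentrality difference/SE, two-sided 0.05:
- Glove use, ICC 0.01, 70 v 80%: 24% with 4 units, about 11% with 3.
- Glove use, ICC 0.001: 61-74% with 4 units, 21-27% with 3.
- Composite, ICC 0.01: 81% with 4 units, about 29% with 3.
- Whole trial (7+7), glove use, ICC 0.01, 70 v 80%: 95%.

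The t reference is not the plan's method: at 4+4 and 70 v 80% it gives 71%, not 85%. It shows that normal-approximation power is optimistic in a stratum where one arm may hold a single unit.

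**The case against.** The strongest reply is that 0.001 is the planning ICC and 0.01 only a variation. At 0.001 the claim holds by the plan's apparent method, and the 8-unit caveat is openly stated one sentence earlier. All of that is true, and none of the plan's individual figures is miscalculated. But the plan chose 0.01, computed with it and stated what it requires. A conclusion that follows directly and drops the condition contradicts it for glove use. The dialysis shortfall against the plan's own 4 units remains at 0.001 as well.

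A second reply is that stratifying by unit type, selecting units on baseline compliance and adjusting for baseline could lower the effective ICC. Section 3 does say that units are matched "based on pre-intervention outcomes of interest to improve power and minimize the impact of measured and unmeasured confounders". This could help, so the percentages above are conditional. However, Section 6.2 credits no such gain. Solving the power formula for 85% (two-sided) shows the effective ICC would have to fall from 0.01 by 31-60% with 4 units or by 54-82% with 3. For example, with 2+2 and 70 v 80%, DEFF = 500 × (0.10/2.996)²/0.185 = 3.01, so ICC = 2.01/499 = 0.0040. Room for matching is also limited at some sites: the candidates listed include "1 ED and 1 inpatient HD unit at UMMC and 4 adult ICUs and 1 ED at Shock Trauma", which leaves no choice of ED at either hospital or of dialysis unit at UMMC.

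A third reply is that Section 6.1 specifies no unit-type test. That stands, and it limits the consequence to interpretation.

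A reader might go further and infer that the trial is underpowered, or that the subgroup claim fails throughout. The documents support neither. Fourteen units comfortably exceed the plan's 8, and by the normal approximation the composite clears 90% in every named type at both ICCs. Nor do the documents show that 0.01 is the truer ICC.

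**Conclusion.** The point holds in a limited form. As an unconditional statement about both outcomes in three unit types, the power claim conflicts with the plan's own 8-unit requirement for glove use at ICC 0.01, and with its 4-unit requirement for dialysis at either ICC. Comparing the unit counts with those requirements needs no outside assumption.

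The size of the shortfall does need assumptions: the normal test, the 10-point gain over a 70-80% baseline, near-balanced allocation within type, and no credit for matching. On those, power falls short of the plan's 85% benchmark by roughly 12-28 points in adult ICU and ED (85 − 73 and 85 − 57) and 25-45 points in dialysis (85 − 60 and 85 − 40). The conclusion survives either sidedness and any number of observations per unit (the latter checked two-sided). The scenarios that pass do so on an approximation that is weak with 3 or 4 clusters, so they are not a sound basis for keeping the claim at unit-type level. The primary inference, the sample size and the design are unaffected.

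**What to change.** In Section 6.2, limit the ample-power sentence to the full 14-unit trial and remove the reference to adult ICU, dialysis and ED. State that results by unit type are exploratory and will be reported with confidence intervals, so that a wide interval is not read as no effect.

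If the sponsor prefers to state unit-type power, give it separately by outcome, ICC and number of units. Name the test and its sidedness, and use a small-sample reference suited to 3 or 4 clusters. The ample-power wording should not be kept for the 3-unit dialysis type under any scenario.

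The change is to wording only and needs no extra units or observations. The cost is a less favourable stated subgroup power.

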The primary outcome, total bacterial colony forming units (CFUs) > 30 of gloved hands, will be compared between the two groups using a comparison of proportions. In this case a one-sided $p < 0.025$ will be statistically significant for noninferiority. We will also compute a two-sided 95% confidence interval for the relative risk of CFUs > 30 comparing direct gloving to HH + gloving, where the upper bound of the confidence interval < delta will be considered statistically significant. In this analysis, we define the non-inferiority margin, or delta, equal to 1.15. We feel (in consultation with microbiologists and HH experts) that if glove reuse (intervention) were found non-inferior to usual care by a 1.15 margin (i.e. a difference of 15%) that this would be enough to lead to change in practice. Robust empirical standard errors will be calculated using generalized estimating equations with an independence working correlation matrix to account for within-site clustering for sample proportions. A secondary analysis will compare groups using CFUs as a count outcome. We will compute a two-sided 95% confidence interval for the relative mean of CFUs on gloved hands comparing the intervention to the usual care group. The upper bound of the confidence interval < delta will be considered statistically significant, where delta is 1.15. The secondary outcomes, presence of pathogenic bacteria and total number of pathogenic and non-pathogenic bacteria present, will be analyzed like the primary outcome.

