Based on pilot data, we anticipate 5% of HCWs in the usual care group (hand-hygiene plus gloves) and 3.5% in the experimental group (direct gloving) to have > 30 CFUs. We define non-inferiority as a relative risk < 1.15 of having > 30 CFUs, comparing the experimental group to the usual care group. That is, delta equal to 1.15. Under these assumptions, 1280 samples (per group) are sufficient for a one-sided test with alpha=0.025 to have 80% power to detect noninferiority.²³ 1280 samples in both groups will result in a total of 2560 samples for the 12-month study period. Spread across the 14 proposed participating units at the 3 healthcare systems (UMMC and STC will share a Research Associate), this is approximately 850 samples per site and 180 samples per participating unit over the 12-month study period. Thus, each site will need to recruit just over 70 HCWs each month to meet the goal sample size. In the pilot study 230 HCWs were recruited and agreed to participate in a single month.

7 Data Collection, Handling and Storage

All data collected will be stored in a relational database in order to digitize the data for analysis. No PHI will be collected. The database will be stored on a shared drive. Data from University of Iowa and Johns Hopkins Hospital will be sent electronically the investigators at the University of Maryland – data from Aim 1A is aggregate unit level data and not-human subjects data; and data from Aim 1B is completely de-identified.

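### Aim 1B: the stated 80% power at 1280 per group is about 74–75% under the written relative-risk margin of 1.15, and the sizing makes no allowance for randomising 14 units

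*Combined protocol and SAP*

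**What the plan says.** Section 6.2 (Aim 1B) gives the assumed rates: "Based on pilot data, we anticipate 5% of HCWs in the usual care group (hand-hygiene plus gloves) and 3.5% in the experimental group". It sets the margin as follows: "We define non-inferiority as a relative risk < 1.15 of having > 30 CFUs". It then concludes that "1280 samples (per group) are sufficient for a one-sided test with alpha=0.025 to have 80% power to detect noninferiority". The planned total is 2560 in the running text, and the header line of the same subsection gives "Local: 866 Worldwide: 2600". On the spread of samples it says "this is approximately 850 samples per site and 180 samples per participating unit over the 12-month study period".

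Section 6.1 (Aim 1B) describes the primary test in two ways. The outcome "will be compared between the two groups using a comparison of proportions" at one-sided p < 0.025. A two-sided 95% confidence interval for the relative risk is also to be computed, "where the upper bound of the confidence interval < delta will be considered statistically significant", with delta equal to 1.15. The analysis is to use GEE robust standard errors, with the clustering described as within site.

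Section 3 (Aim 1A) fixes the unit of randomisation: "Each unit will be randomly assigned to the intervention or usual care group". The primary Aim 1B analysis in Section 6.1 compares samples by that allocation. The Aim 1A sizing in Section 6.2 uses intraclass correlations of 0.001 and 0.01. The Aim 1B sizing uses none.

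**The concern.** There are two separate problems.

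1. **Scale.** The margin and the confidence-interval rule are on the relative-risk scale, so the stated power should be the probability that the upper bound for the relative risk falls below 1.15 under 5% versus 3.5%. It is not.
2. **Clustering.** Samples from one unit share staff, practices and environment, and the unit is what is randomised. A sample size for independent observations overstates the information in about 183 samples per unit.

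The 80% is the only justification given for the Aim 1B sample size. Aim 1B is the part of the study meant to confirm that direct gloving does not increase glove contamination. If it fails to show non-inferiority, readers who believe the power was 80% will read more into that failure than they should.

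**Working it through.** **Inputs.** Usual-care rate p_c = 0.05; direct-gloving rate p_t = 0.035 (true RR 0.70); margin RR 1.15; one-sided alpha 0.025; n = 1280 per group (all Section 6.2, Aim 1B). There are 14 units, so m = 2560/14 = 182.9 samples per unit. ICCs of 0.001 and 0.01 come from the Aim 1A sizing.

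**Step 1: reproduce the plan's figure.** Convert the margin to an absolute one at the assumed 5% rate: 1.15 × 5% − 5% = 0.75 points. The distance from the assumed difference to the margin is 0.0075 + 0.05 − 0.035 = 0.0225. For the Farrington–Manning score test of the difference, the restricted rates are 4.72% and 3.97%. The null SD term is √(0.0472×0.9528 + 0.0397×0.9603) = 0.2882. The alternative SD term is √(0.035×0.965 + 0.05×0.95) = 0.2851.

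n = [(1.96×0.2882 + 0.8416×0.2851)/0.0225]² = 1279.4, so 1280 per group, with power 80.0%.

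This matches exactly. The unpooled Wald version of the same test gives 1261 per group and 80.6% power at 1280. So the stated figure follows from a fixed 0.75-point margin that treats the 5% control rate as known.

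**Step 2: power of the written relative-risk rule, independent samples.** For the log-RR Wald interval:

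- V = 0.965/0.035 + 0.95/0.05 = 46.57
- D = ln 1.15 − ln 0.70 = 0.4964
- SE at 1280 per group = √(46.57/1280) = 0.1907
- Power = Φ(0.4964/0.1907 − 1.96) = Φ(0.643) = 74.0%
- n for 80% = (1.96 + 0.8416)² × 46.57/0.4964² = 1483.2, so 1484 per group

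| Method on the RR margin | 1280 per group | 1300 per group | n per group for 80% |
|---|---|---|---|
| Log-RR Wald interval, formula | 74.0% | 74.6% | 1484 |
| Same rule, exact binomial enumeration | 74.5% | 75.2% | about 1450 (80.3%) |
| Farrington–Manning score test of the ratio, exact enumeration | 74.6% | 75.4% | 1465 (formula) |

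The 1300 column corresponds to the stated worldwide total of 2600. If the comparison of proportions in Section 6.1 is read as a score test against the only written margin, it has about the same power as the interval rule.

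**Step 3: clustering by randomised unit.** DEFF = 1 + (m − 1) × ICC. The plan gives no ICC for CFU > 30, so the values below are an assumption borrowed from Aim 1A.

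| ICC (assumed) | DEFF | Power, RR rule | Power, 0.75-point difference (Wald / score) |
|---|---|---|---|
| 0 | 1.00 | 74.0% | 80.6% / 80.0% |
| 0.001 | 1.18 | 66.8% | 73.8% / 73.1% |
| 0.002 | 1.36 | 60.6% | – |
| 0.005 | 1.91 | 47.0% | – |
| 0.01 | 2.82 | 34.1% | 39.0% / 38.2% |

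An ICC of 0.01 is severe at this prevalence: the between-unit SD would be √(0.01×0.05×0.95) = 2.2 points around a 5% rate. These are simple design-effect figures that ignore stratification and matching.

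**Step 4: few units.** A beta-binomial simulation (200,000 runs) assumed 7 versus 7 units of 183, with unit-level robust standard errors for the log RR. ICCs were 0, 0.001 and 0.01. Uncorrected errors met the rule 79%, 72% and 43% of the time, but with one-sided error of 4.7–4.9% instead of 2.5%. With a k/(k − 1) variance correction and t on 12 df, error returned to about 2.5% and power was 67%, 60% and 31%.

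**The case against.** The strongest reply is that the sponsor's number is not a slip. As Step 1 shows, it is exactly right for a score test on the difference scale. Section 6.1 names a comparison of proportions first and glosses the 1.15 margin as a 15% difference, and 0.75 points follows from two written numbers. The sizing sentence also cites a reference that the public text does not list, so the method may be specified there. This stands as an account of where 1280 came from: it makes the first problem a mismatch between the sizing scale and the decision scale. It does not rescue the 80%. The absolute margin is never stated, both sections define delta as a relative risk of 1.15, and the interval rule estimates the control rate that the sizing takes as known.

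On clustering, the reply is that robust standard errors are already planned and that the ICCs are borrowed from a different outcome. Robust errors correct the variance estimate but do not restore power. The second half is fair: the size of the loss is unknown, and the lower end of the table rests on a severe assumption. The 7 versus 7 split is also an assumption, since the strata described in Section 3 hold 4, 3, 4 and 3 units and two of them cannot balance. The within-site wording in Section 6.1 is not relied on here; the point rests on the randomisation of units.

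**Conclusion.** The concern holds. Under the plan's own rates and its only written margin, 1280 per group gives 74–75% power with independent samples, 5 to 6 points below the stated 80%. The stated total of 2600 gives about 75%. This part needs no assumption beyond the plan's inputs.

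The sizing also contains no design effect, although units are randomised, and this is true on either scale. How much power that costs cannot be fixed from the documents. With the Aim 1A ICCs as an assumption, the relative-risk rule has about 67% (0.001) or 34% (0.01), and the difference scale about 73–74% or 38–39%. All these figures also depend on direct gloving being truly better (3.5% against 5%). If both rates were 5%, the relative-risk rule would have about 13% power at 1280 per group even without clustering.

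**What to change.** In Section 6.2, Aim 1B:

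1. Name the scale and test on which the sample size is calculated, and make it the one used for the decision in Section 6.1. If an absolute margin is intended, state it in both sections.
2. For the relative-risk rule, replace the unqualified 80% with about 74–75% without clustering at 1280 to 1300 per group.
3. Add power with a unit-level design effect over a stated and justified ICC range for CFU > 30.

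The cost is protocol wording and a less favourable stated power. The correction itself needs no extra samples, visits or units. Restoring 80% on the relative-risk rule would be a separate decision, needing about 1450 to 1484 per group before clustering.
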